## 5.1. Population to be Studied

Patients older than 65 years AND more than 2 comorbid conditions AND/OR more than two requirements for unscheduled urgent care in previous year AND/OR medium or high frailty score. The study participants will live in the South Uttlesford area of East Anglia, in the north of the West Essex CCG territory unless we are unable to recruit sufficient patients, in which case the study area may be extended.

#### 5.2. Method

The study will use patient data held in care home and GP records to identify potential participants. Health professionals working for the participating care homes or GP surgeries will then use inclusion and exclusion criteria to select patients for invitation to join the study. In the care home phase (Phase 1), the care home manager will sign and hand an invitation letter and Patient Information Leaflet to the potential participants whom they have identified and ask them to sign an attached form giving consent to be approached by the research team for informed consent. In Phase 2, the primary care phase, GP surgery staff will send the invitation letter and Patient Information Leaflet to potential participant and process the returned forms, booking informed consent appointments. The research team is seeking the support of the North Thames Clinical Research Network in parallel with the application to the HRA/REC; if successful, staff from the CRN will support the recruitment and consenting process in Phase 2 only.

The study cohort will be taken from those who have needed most urgent care and who have the largest number of comorbidities, as defined by the inclusion and exclusion criteria above.

**Phase 1** of the study will be conducted with up to 100 participants residing in care homes. Either Health Research Assistants employed by the research team or local care home employed professionals (the choice between these two to be at the care home's discretion) will use connected medical devices to collect data from the cohort at twice-weekly intervals for twelve weeks. In this phase **all devices will be used with all participants**.

NHS activity data will be obtained from the records held in GPs' clinical systems at the end of Phase 1 to enable models to be constructed that will test the study hypothesis and allow the mapping of chronic conditions to device types to be optimised. This will mean that in **Phase 2**, participants will only be asked to use devices that have been proved in **Phase 1** to be effective at collecting useful data relevant to their specific set of co-morbidities.

In **Phase 2**, a total of 500 participants will be enrolled who meet the study inclusion criteria. Any participants from **Phase 1** who want to continue to have their health measurements taken will be permitted to proceed to **Phase 2** and the remained, up to a total of 500, will be recruited from their GP surgeries and asked to participate from their own homes. Continuing care home residents will continue to receive twice-weekly visits from the project's Health Research Assistants (or care home employed

professionals, as appropriate); those participating in the study from their own homes will do so autonomously using the smartphone, the Reassure OneApp application loaded onto the smartphone, and a set of devices appropriate to their co-morbidities. They will be shown how to take their health measurements during an initial visit from one of the project's Health Research Assistants, and the Reassure OneApp application will also display reminders of how to do this. In addition to this, Health Research Assistants will be available to make visits to the participant's home to support them in collecting their health measurements at the request of the participant.

The medical devices will send back data to central server facilities in Cambridge, UK to L2S2's patient management system that will automatically adjust the visit frequency for each patient and prompt compliance to minimise dropout.

At the end of **Phase 2**, NHS activity data will be obtained from the participants' GP to allow correlation between the actual recorded instances of requirement for unscheduled care and the data collected in the trial from the medical devices.

Machine learning and statistical analysis will be used to determine the validity of using home collected and care home collected data from smart medical devices to predict future likelihood of requirements for unscheduled urgent care.

## 5.3. Summary of findings from previous studies

Studies have previously demonstrated the ability of telemedicine to decrease use of emergency departments and hospitalisations among vulnerable populations such as children and the elderly [9-12]. However, existing tools and guidelines were developed for the identification and management of individual health issues, verticalising problems. Yet, a complex patient suffers from multi-morbidity and polypharmacy. Consequently, they are often treated via a conglomeration of juxtaposed guidelines, taking more than 10 drugs a day with no certainty of efficacy [13]. Hence, the current disease-focused approach has been repeatedly subjected to scrutiny, calling instead for a patient-centred approach focused on personalised appropriateness and adherence [13,14]. The impact of a high-intensity telemonitoring model for holistic geriatric health (identification of acute disease & chronic exacerbations) implemented in senior communities has been documented by Shah et al [15,16]. Building upon this preliminary evidence, the study will conduct a structured evaluation of the ability of a holistic data collection process in the community to enable early detection of unplanned health needs in complex patients such as the elderly. Moreover, as evident from data submitted by the Authority, in West Essex, people over 65 constitute the majority of patients with complex healthcare needs and lead to the majority of expenditure on hospital admissions (Figure 2).

Figure 1 Analysis of complex patients in West Essex CCG

[figure not shown]
[figure not shown]

Figure 2

## 5.4. Risks

L2S2 perform risk analyses to ISO 14971 as part of the company ISO 13485 Quality Management System (QMS). Risks for this project are listed below:

001 Risk: Cross Infection between patients

Hazard: Bacteria, spores and viruses could be transferred by a device if reused

Hazardous Situation: Inadequate cleaning / disinfection / sterilization

Harm: Pathogens could be transferred between patients

Likelihood: Frequent

Severity: Serious

Risk Assessment: Serious

Mitigation: All devices will have a record entry in the master device database that will show cleaning status and allow cleaning process to be tracked.

Cleaning / Disinfection / Sterilisation will be performed to formal procedures and tracked

Devices that enter or contact mucous membranes will either be single use or will be returned to the company for formal cleaning between each reuse.

Cleaning processes will be audited once per month.

Residual Risk: Acceptable

002 Risk: Contact Dermatitis

Hazard: Patient's skin reacts with surfaces of any of the medical devices

Hazardous Situation: Allergic or rash reaction happens after wearing / touching the devices

Harm: Discomfort, rash or swelling requiring intervention

Likelihood: Rare

Severity: Minor

Risk Assessment: Reasonable

Mitigation: Patients will be asked if they have a history of adverse effects from any contact materials as part of the study inclusion criteria and throughout the study. The HCAs will check the patients at each visit, and to minimise any effects, the device will be withdrawn from the patient if any adverse effects are detected.

Residual Risk: Acceptable

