## 10.5. Maintenance and storage of devices

L2S2 opens, tests and charges all purchased devices on arrival in a sterile facility in its premises in Cambridge. The devices are then turned off and stored in labelled plastic bags. When devices are to be despatched to participants their charge state is checked again and software is put on the device. The sealed devices are sent by courier to the HRAs (or care homes) who will assign each device to a participant. This is done with the device in the sealed bag which is not opened until the device is first used by the participant.

When the device needs to be taken back, the patient, HRA or care home employed professional will place the device(s) in biological control bags and return them to the Cambridge site either for cleaning, disinfecting or sterilising according to approved procedures set out in ISO13485, or for safe disposal if the device is not to be reused. Devices that can be cleaned in the field like the blood pressure meter are assessed to be low risk and may be cleaned with DiffX wipes or spray. The HRA will use a cleaning protocol wizard on a section of the Reassure OneApp application only visible to research team staff to provide a complete, auditable trail of cleaning / sterilisation procedures.

The HRA will record the condition of the devices at each visit and will clean them / remove them as appropriate to ensure safety is not compromised.

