#### 27. Appendix E COVID-19 Procedures

Specific COVID-19 procedures have been added to the monitoring app and the care home staff research assistant's SOP.

Phase 1 of the trial was suspended because of the onset of COVID-19 in the UK. It was clear in February 2020 that visiting care homes would be unsafe and the UK was put into lockdown by the government on 23 March to attempt to limit the spread of coronavirus.

It appears that the government will gradually lift lockdown rules from June 2020 but it will be necessary to continue shielding of vulnerable participants for the foreseeable future. The study cohort is focussed on the over 65s with multiple co-morbidities and this group will be particularly susceptible to harm by COVID-19. It would not be possible to visit care homes under the government guidelines that state that care homes should restrict all non-essential healthcare visits.

The trial protocol has been revised to avoid the need for physical contact with the care homes and participants.

The Reassure app used to collect data in this trial has been updated to include secure video conferencing and safety features that make it possible to conduct the trial remotely and yet still obtain reliable data. The app is already in use in NHS hospitals to allow remote monitoring of participants at home during COVID-19.

Before COVID-19 it was intended that staff in some care homes would collect the participant data. Now only care homes that will allow their staff to collect data will be included in the trial. It is proposed that the care home staff will receive training via the app video link to enable them to use the devices safely and achieve good data quality.

The video will not be used for or with participants, only for staff assistance and training.

Each time it is used, the opening screen of the app will assess whether the participant is displaying the symptoms of COVID-19 infection.

It does this by requiring the staff member to follow an on-screen protocol as follows:

- At the start of each shift the staff member shall record their own temperature and answer COVID symptoms questions. If COVID is suspected, the app will prevent further use by that staff member until a negative result from a formal COVID-19 test is entered or until seven days have passed from the last symptoms. If the staff member is not suspected of having COVID0-19 the app continues as before.

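### The only described record of in-home device cleaning is restricted to research-team staff, while Phase 1 now runs only in homes whose own staff operate the devices

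*Protocol*

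**What the plan says.** Section 5.4 of the protocol scores cross infection between patients as "Likelihood: Frequent" with Serious severity, and then rates the residual risk Acceptable. Four mitigations stand between the two ratings:

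- a central record: "All devices will have a record entry in the master device database that will show cleaning status and allow cleaning process to be tracked";
- formal cleaning: "Cleaning / Disinfection / Sterilisation will be performed to formal procedures and tracked";
- for devices that touch mucous membranes, that they "will either be single use or will be returned to the company for formal cleaning between each reuse";
- an audit: "Cleaning processes will be audited once per month".

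Section 10.5 says how cleaning in the field is recorded: "The HRA will use a cleaning protocol wizard on a section of the Reassure OneApp application only visible to research team staff". The same section gives the HRA the job of noting device condition at every visit and of cleaning or removing devices. It also lets the patient, the HRA or a care home professional bag devices and send them to Cambridge for cleaning.

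Section 5.2 offered two kinds of Phase 1 operator, HRAs "or local care home employed professionals (the choice between these two", with the decision left to the home. Appendix E then removes the first option in practice: "Now only care homes that will allow their staff to collect data will be included in the trial". It explains that the revision is meant to avoid physical contact by the research team. Its only statement on device cleaning concerns the thermometer, which is left to the home's own hygiene procedures.

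**The concern.** The restriction on the wizard fits a study in which a research-team HRA visits with the devices. Appendix E describes a different study: care home employees handle the devices and the research team stays away. Sections 5.4 and 10.5 do not reflect that change. If the access rule is followed as written, the people who clean devices in the home cannot record it, and the people who can record it are not there.

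This bears on the risk rating. The step down to Acceptable leans in part on knowing that cleaning took place, and the participants are residents whom Appendix E itself describes as especially vulnerable to COVID-19. If in-home cleaning leaves no entry, the central record may not show whether a device was cleaned before its next use, and the rating claims support that the text does not provide.

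**Working it through.** There is no figure in the plan to reproduce. The check compares who performs each control with who is in the home.

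**Step 1. Which controls depend on someone in the home?**

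| Control in 5.4 | Operator named in the protocol | Position under Appendix E |
|---|---|---|
| Single use, or return to the company, for mucous-membrane devices | Return: patient, HRA or care home professional (10.5) | Still workable |
| Formal, tracked cleaning at Cambridge | Central site (10.5) | Still workable |
| Formal, tracked cleaning in the home | HRA only, through the restricted wizard (10.5) | No stated operator |
| Master device database | Not stated | Exists, but no stated route brings in-home cleaning into it |
| Monthly audit of cleaning processes | Not stated | Exists, but no stated route supplies in-home cleaning records |

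The table has five rows for four mitigations because tracked cleaning splits into a central part and an in-home part.

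**Step 2. Is the HRA a different person from the care home professional?** In this protocol, yes. When devices are returned, 10.5 lists the patient, the HRA and the care home professional as separate roles, but it names only the HRA for the wizard and the condition check. Sections 5.2, 7 and 10.8 draw the same line between research-team assistants and the home's own employees.

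**Step 3. Is cleaning in the home actually foreseen?** Yes. Section 10.5 provides for wiping or spraying low-risk devices in the field and gives the blood pressure meter as an example. Section 7 describes a standard kit carried by the HRA, which suggests sharing. Section 10.5 also says each device is assigned to a participant, which suggests the opposite. The documents therefore do not settle how often a device passes from one resident to another.

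**Step 4. Does Appendix E supply another record?** Not in its text. The thermometer sentence mentions no record. The app's time-stamped log is said to cover all actions, but cleaning is not named.

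**Step 5. Scale.** Inputs from 5.2: up to 100 residents, two sessions a week, 12 weeks.

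Sessions at most = 100 x 2 x 12 = 2,400.

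This assumes that all 100 places are filled for the full 12 weeks. Section 7.1 ends a resident's follow-up at exacerbation, dropout or study end, so the real number would be lower unless every place is refilled at once. It counts sessions. The hazard in 5.4 arises on reuse, and the number of reuses cannot be derived from the protocol.

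**Step 6. When did the gap arise?** Sections 5.2 and 7 already allowed staff-run homes, so the gap existed for those homes before COVID-19. Appendix E made the staff-run home the only kind. It can also reach Phase 2, because 5.2 lets continuing residents be measured by care home professionals.

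**The case against.** The strongest reply is that this is a cross-reference left un-updated and not a failed safeguard. A reader might infer from the mismatch that the cross-infection control cannot work in Phase 1, or that no in-home cleaning will be recorded at all. The documents do not support either reading, for these reasons:

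- The rating rests on four mitigations, and none is stated to depend on the wizard. Care home staff are expressly allowed to return devices to Cambridge.
- What 10.5 restricts is a section of the app used to make entries. The protocol does not say who can see or update the master device database.
- Appendix E refers to an operating procedure for care home staff acting as research assistants, and section 14 promises procedures for all aspects of the study. Those procedures are not shown and may grant access or set up another record.
- The monthly audit is of cleaning processes, not of wizard entries, so it would not necessarily have nothing to examine.
- Appendix E adds infection controls of its own: screening of staff and residents, temporary exclusion, a separate device set for confirmed cases and a lock on the original devices. Section 7.2 also requires cleaning before a device goes to another participant.

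All of this stands, and it limits the point to one part of one mitigation. It does not remove it. The access rule in 10.5 is explicit, the named operator is no longer on site, and a procedure that gave care home staff access would contradict the protocol's own sentence. The additional controls in Appendix E deal with suspected or confirmed COVID-19. The risk in 5.4 covers bacteria, spores and viruses in general.

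**Conclusion.** The point holds in a limited form. As the protocol is written, cleaning done in the home has no person who is both present and able to enter it in the described trail, and the device-condition check at each visit is likewise assigned to someone who is absent. The Acceptable rating in 5.4 relies partly on tracked cleaning, so for staff-run homes it has less behind it than it claims. The remaining controls still operate, although the database and the audit have no stated source of in-home cleaning data.

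The size is bounded only loosely: up to 2,400 Phase 1 sessions, with an unknown number of device transfers between residents. The conclusion assumes that the access restriction means what it says and that HRAs do not visit the homes. An operating procedure that is not shown could close the gap in practice, but the protocol would still need to agree with it. The effect is on participant safety and on the credibility of the risk assessment; the documents give no basis for claiming an effect on the primary analysis.

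**What to change.** Reconcile sections 5.4 and 10.5 with Appendix E, including its thermometer sentence, so that they describe the same operator and the same record. In particular:

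- extend access to the cleaning wizard and the device-condition record to the care home professionals who operate the devices, and name them in 10.5 beside the HRA;
- state how an in-home cleaning entry reaches the master device database and the monthly audit; the app's existing time-stamped log could carry it;
- review the residual rating for cross infection in staff-run homes. Section 15 already provides for reviewing the risk assessment after significant protocol changes, so no new mechanism is needed.

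This changes who may record cleaning. It proposes no cleaning method or frequency. The cost is an app permission change, one item in the staff video training, an amendment to two sections and the appendix, and a little staff time per session.

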### 5.5. Rationale for undertaking the study

In 2019 there has been a step change in the costs of personal medical devices, ease of use, cost of connectivity and machine learning capabilities. These changes render the technology more affordable by the NHS and more usable by elderly people. In 2018, the Emergency Care Data Set (ECDS) was introduced to all A&E departments in England and for the first time comprehensive outcomes based data on

Clinical Research Protocol CONFIDENTIAL

L2S2 ltd Page 13 of 38

attendance at A&E departments is available. Together the changes in technology and availability of high-quality reference data make this study possible.

Participants will be selected who are likely to exacerbate during the trial period and therefore the size and duration of the study are considered adequate to test the hypothesis thoroughly.

#### 6. OBJECTIVES AND OUTCOME MEASURES

Objectives	Outcome Measures	Timepoint(s) of evaluation of this outcome measure (if applicable)
Primary Objective The purpose of the study is to find out the confidence of correlation and its statistical significance	The correlation confidence level for exacerbation prediction from data collected from medical devices in the participant's home or care home with actual attendance data obtained from GP surgeries.	End of study (study is non-interventional)
Secondary Objectives  1. Determine drop out percentage	1. Dropout Percentage: Number of readings taken by patients compared to their agreed plan.	End of study
2. Determine relationship between frailty and ability to adhere to plan	2. Correlation between adherence to agreed plan and the participant's frailty score.	
3. Determine relationship between number of co-morbidities and resource required.		

4. Determine effectiveness of different devices as predictors of exacerbation by complication group.

- 3. Number of visits required for each complication group by number of comorbidities
- 4. Correlation of each type of device for each complication group as a predictor of exacerbation (i.e determine which device(s) are most useful).

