#### 7. STUDY DESIGN

The study type will be observational, collecting data from wearables and remote monitoring medical devices to determine correlations with primary data collected from GP surgeries attended by the participants in the course of the study.

Participants will be recruited by West Essex CCG from patients in their region who meet the study inclusion criteria.

The first phase of research with up to 100 participants will be conducted in care homes with twice-weekly visits from Health Research Assistant's (HRA) employed by the research team, equipped with a standard kit of medical devices who will ensure the devices are used appropriately to maintain data quality and who will monitor the effectiveness of the electronic devices. If care homes would rather be trained to undertake these duties using their own staff, the research team will train them and remunerate the care home for these staff costs.

The second phase of 500 participants will be conducted in participants' homes and care homes with visits from a research team HRA to ensure safe and effective use of condition specific wearable and monitoring devices when this is requested. Visit frequency will be automatically adjusted by feedback from the monitoring systems. (Typically once per week.)

The electronic devices will provide primary medical data as well as metadata regarding battery charging behaviour, adherence to study procedures, effect of active compliance management and direct feedback from the participants. The visit frequency will be adjusted to ensure maximum effectiveness of the equipment and to maximise economic benefit to allow a 'best practice' baseline to be established.

The medical devices issued to each patient will be determined by observations and data collected by the HRAs in conjunction with baseline data derived from GP data.

In **Phase 1**, all devices will be used to take measurements from all participants. Devices will be issued to HRAs who will use them to ensure correct use and valid data.

In **Phase 2**, devices will be allocated to participants based on data gathered in **Phase 1**. It is anticipated that this will demonstrate the best combinations of devices for recording health measurements for different sets of co-morbidities, and prove or disprove the following assumptions:

Clinical Research Protocol L2S2 ltd Page 16 of 38

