#### 12. STATISTICS AND ANALYSIS

## 12.1. Statistical Analysis

Studies to measure interventions are designed using power calculations that minimise the risk of not finding a difference between treatments if one exists (a type II error).

In a purely observational study, such calculations are less relevant, but the study design still needs to provide assurance that sufficient data will be collected to but for this study.

This is mainly achieved by ensuring that the target population has a high event frequency of the index condition — in this case deterioration of healthcare such that hospital admission would be necessary. The mean time of residence for a patient in nursing home care is approximately 15 months, but with half the residents dying in the first six months of residence.

https://www.geripal.org/2010/08/length-of-stay-in-nursing-homes-at-end.html?m=1

Following the protocol described below, a cohort of elderly people (>65 years) living independently and in care/nursing homes, with

- a moderate or high degree of frailty,
- comorbidities as defined in the appendix using standardised NHS list
- a history of regular NHS activity will be identified.

Stage 1 of data collection will feature a universal monitoring plan across for nursing home residents and, following analysis, Stage 2 of data collection will ensure measurements are collected with frequency and using devices appropriate to the needs of different participants by tailoring the frequency and type of monitoring to the needs of the condition and patient.

To provide assurance that the sample size is likely to provide sufficient event frequency, a power calculation was performed (Jones et al. 2003).

Data provided by the West Essex CCG was used to explore different incidence rates of index episodes of health deterioration requiring NHS treatment in the target population as defined above.

As 50% of the nursing home population is likely to die within six months of admission, the recruitment of existing nursing home patients means event prevalence rates of 55% is a conservative estimate.

The lowest acceptable sensitivity of the algorithm was assumed to be 85% (SN) and the lowest acceptable specificity – 80% (SP). A confidence interval of 5% (W) was selected. The required sample size can be determined via the sensitivity or the specificity limit, depending on priorities:

$$N(SN) = \frac{TP + FN}{P} = 1.96^2 * \frac{(SN(1 - SN))}{W^2}$$

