## 28. Appendix F Informing the Care Home Staff to take Action Based on Device Readings

Readings from medical devices recording vital signs can be used together with a clinical knowledge of a patient's conditions to provide an informed view of whether a patient is suffering an exacerbation that should be investigated. An individual reading from a vital signs monitoring device may cause unnecessary worry and not indicate a serious condition for a particular patient. Care home staff are not medically qualified and will not in general be able to interpret occasional out of bounds readings.

However, values from some devices that give a reliable indication irrespective of the patient's specific condition may be used to aid common sense judgment that action should be taken. The medical device monitoring phone is programmed to show vital signs according to the NEWS2 scoring system used in hospitals to give an 'at a glance' display of a patient's overall status. The SpO2 alerts and colour scheme used is that of Scale 1 in the NEWS2 scoring system. SpO2 on its own is not considered to be a safe warning sign as medical knowledge of the patient's condition is needed to decide on a suitable alert threshold.

In Reassure, values that will cause a red alert to be triggered to help the care home worker decide if a patient's condition might require attention are as follows:

<= 40 or >= 131 bpm (at rest)

Respiration <= 8 or >= 25 BPM

Temperature >= 38.0°C (COVID-19 threshold)

Systolic Blood Pressure <= 90 or >220 mmHg

Pulse

ECDS_UniqueID	Sort1	Sort2	ECDS_Group	ECDS_Description	SNOMED_Code	SNOMED_Description	Notes
						Hypertensive disorder, systemic	
2018111100	11	11	Circulation / blood	Hypertension	38341003	arterial (disorder)	-
2018111500	11	15	Circulation / blood	History of anticoagulant therapy	161647008	History of anticoagulant therapy (situation)	_
2018112100	11	21	Circulation / blood	Ischaemic heart disease	414545008	Ischemic heart disease (disorder)	_
2018113100	11	31	Circulation / blood	Cardiac pacemaker in situ	441509002	Cardiac pacemaker in situ (finding)	_
2018114300	11	43	Circulation / blood	Congestive heart failure	42343007	Congestive heart failure (disorder)	_
2018114500	11	45	Circulation / blood	Left heart failure	85232009	Left heart failure (disorder)	-

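### The primary outcome pools care-home and own-home participants in one correlation; if event rates also differ by setting, it can be significant with no predictive value inside either setting

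*Protocol*

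**What the plan says.** Section 6 gives the primary objective as to "find out the confidence of correlation and its statistical significance". The outcome is a single confidence level, for predicting exacerbation, of the correlation of "data collected from medical devices in the participant's home or care home with actual attendance data obtained from GP surgeries". No split by setting is named. The only split is a secondary one, by device and complication group. The synopsis speaks of correlations in the plural, but not by setting either.

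Section 7 states: "The second phase of 500 participants will be conducted in participants' homes and care homes". The two settings are run differently:

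- **Care home (section 5.2):** "Continuing care home residents will continue to receive twice-weekly visits from the project's Health Research Assistants", or from care-home staff. Appendix E now limits the trial to care homes whose own staff collect the data.
- **Own home (section 5.2):** "those participating in the study from their own homes will do so autonomously using the smartphone". Section 7.1 adds assistant visits on request, about weekly, and section 10.9 lets the returned data set the measurement interval.
- **Alerts (Appendix F):** there are "values that will cause a red alert to be triggered to help the care home worker decide" whether a resident needs attention. No such alert is described for people at home.

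On event rates, section 12.1 argues that "the recruitment of existing nursing home patients means event prevalence rates of 55% is a conservative estimate". Both planning tables in that section use 35% a month: Stage I for care homes, Stage II for the two settings together.

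**The concern.** Setting is linked to how a reading is obtained and may be linked to how often people need unscheduled care. If both links exist, a reading that merely differs in level between settings will correlate with attendance over the pooled sample, even if it says nothing about who deteriorates within a care home or among people at home. Section 6 asks for the correlation and its significance, so this could be reported as evidence of prediction. The service suggestions in section 12.5 rest on whether prediction works, and a single pooled figure does not show whether it works for people at home.

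**Working it through.** **The plan's own figures.** The N(SN) row of section 12.1 is 1.96² × SN(1 − SN) / W² / P, with SN = 0.85 and W = 0.05. At P = 0.35 this is 3.8416 × 0.1275 / 0.0025 / 0.35 = 559.8, against 560 stated. Stage II episodes are 35% of 500, 464 and 430, stated as 175 + 162 + 151 = 488. Both reproduce, and both use one rate for everybody.

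**Inputs for the check.**

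- Setting split 100 care home and 400 own home: the most residents that section 5.2 allows to continue (Phase 1 has up to 100), with the rest recruited at home.
- 35%: both planning tables. 55%: the nursing-home argument in section 12.1. Setting 55% in care homes against 35% at home is an assumption; 45% v 35% is a milder one.
- Difference in mean reading between settings, d = 0.5 or 1 SD: an assumption with no source in the protocol.
- One reading summary and one yes/no event per participant, two-sided 5% test: assumptions, since section 6 states neither unit nor level.

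**Correlation from setting alone.** Let w be the care-home share, pc and ph the event rates in care home and own home, and p the overall rate. With no association inside either setting,

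r = w(1 − w)(pc − ph)d / √{[1 + w(1 − w)d²] p(1 − p)}.

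For 55% v 35%: w(1 − w) = 0.16, p = 0.39 and p(1 − p) = 0.2379.

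- d = 0.5: r = 0.016 / √(1.04 × 0.2379) = 0.032.
- d = 1: r = 0.032 / √(1.16 × 0.2379) = 0.061.

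For 45% v 35%, d = 1: p = 0.37 and r = 0.016 / √(1.16 × 0.2331) = 0.031.

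The critical |r| at n = 500 is tanh(1.96 / √497) = 0.088.

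**Simulated false significance** (8,000 runs, Fisher z). The stratified test combines the two within-setting z values: [zc(nc − 3) + zh(nh − 3)] / √(nc + nh − 6).

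| Rates, care home v own home | d (SD) | r | Pooled | Stratified |
|---|---|---|---|---|
| 35% v 35% | 1 | 0 | 4.7% | 4.7% |
| 45% v 35% | 0.5 | 0.016 | 6.8% | 5.2% |
| 45% v 35% | 1 | 0.031 | 10.5% | 5.2% |
| 55% v 35% | 0 | 0 | 4.8% | 4.8% |
| 55% v 35% | 0.5 | 0.032 | 11.1% | 4.8% |
| 55% v 35% | 1 | 0.061 | 27.2% | 4.7% |

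Inflation needs both a rate difference and a reading difference. Reversing the split to 400 care home and 100 own home gives 25.9% in the last row.

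**Size as discrimination, 55% v 35%.** The care-home share is 0.2 × 0.55 / 0.39 = 0.282 among people with an event and 0.2 × 0.45 / 0.61 = 0.148 among those without. AUC = 0.5 + (0.282 − 0.148)[Φ(d/√2) − 0.5], which is 0.519 at 0.5 SD and 0.535 at 1 SD.

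**Precision by setting**, half-width 1.96 × √(0.85 × 0.15 / events):

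- 100 participants at 35% (35 events): 0.118.
- 100 participants at 55% (55 events): 0.094.
- 400 participants at 35% (140 events): 0.059.
- 400 participants at 55% (220 events): 0.047.
- All 500 at 35% (175 events): 0.053.

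**The case against.** The strongest reply is that the protocol documents no rate difference. The 35% is its own care-home planning figure in Stage I, and at a common 35% there is no inflation. The 55% comes from six-month mortality while 35% is applied monthly, so pairing them mixes time bases. This stands: 55% v 35% is an illustration only. A wider gap is tempting too; 55% v 30% with 1 SD gives 41%. But 30% is only the lowest incidence in the sample-size table, not an own-home rate.

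Other points stand in part:

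- **Participant norms.** Section 10.7 has software establish each person's norms, which may remove some of the level shift. Nothing says the primary correlation uses only departures from those norms.
- **Planned care-home result.** Section 12.2 already plans an interim report from the care homes alone, although section 12.3 says no analysis takes place before the study is complete. It is not the end-of-study primary outcome and gives no own-home result.
- **Accuracy limits.** Section 12.1 takes 85% sensitivity and 80% specificity as the lowest acceptable. A single cut-off at those limits has an AUC of (0.85 + 0.80)/2 = 0.825, so an AUC near 0.52 to 0.54 could not pass for success. But section 6 ties the objective to correlation and significance, not to those limits.
- **Analysis plan.** Adjustment for setting may be in an analysis plan that is not shown. The point is therefore confined to the pooled definition that section 6 itself states.

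**Conclusion.** The point holds as a possible confounding of the primary measure by setting. Section 6 pools two groups that differ by design in operator, measurement frequency and alerts. Those differences alone create no false correlation; event rates must differ as well, and alerts matter here only so far as they change attendance. Under the assumed inputs, false significance rises from 5% to about 11% to 27% at 55% v 35% and to about 10% at 45% v 35% with 1 SD.

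A reader might infer that the settings are known to differ in event rate, or that the trial would report prediction where none exists. The protocol supports neither. It gives no rate by setting, the expected correlations lie below the critical 0.088, and even at 55% v 35% some 73% to 89% of such trials show no false result.

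A reader might also infer that machine learning would simply learn the setting. If it recovered setting perfectly, r would be 0.164, the AUC 0.567, and the pooled test would be significant in about 95% of trials at 55% v 35%. That is an upper bound; nothing in the protocol shows the model would do this.

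This is a cheap improvement worth making, not proof that the pooled result will be false.

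**What to change.** First reconcile the setting split. Section 5.2 implies at most about 100 care-home participants and the rest at home. The Stage II table in section 12.1 appears to place 400 under nursing/care and 100 under independent living, though its header is broken in the text available.

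Then, in sections 6 and 12.1:

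- make the primary measure a setting-stratified (within-setting) estimate;
- report care-home and own-home results separately;
- keep the unstratified pooled value as secondary;
- state the precision for each setting under both rates. With 100 in care homes, the half-width at 85% sensitivity is about ±12 points at 35% and ±9 at 55%. With 400 at home, it is about ±6 at 35%. If fewer residents continue, the care-home interval is wider.

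The cost is analysis wording only: setting is already known, and no extra participants or data are needed. The downside is a wide interval for the smaller setting.
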